The protocol, informed consent form(s), recruitment materials, and all participant materials will be submitted to the Institutional Review Board (IRB) for review and approval. Approval of both the protocol and the consent form must be obtained before any participant is enrolled. Any amendment to the protocol will require review and approval by the IRB before the changes are implemented to the study. In addition, all changes to the consent form will be IRB-approved; a determination will be made regarding whether a new consent needs to be obtained from participants who provided consent, using a previously approved consent form.

1 PROTOCOL SUMMARY

1.1 SYNOPSIS

Title:	Investigating Central Neurophysiologic Correlates of Non-motor Symptoms of Parkinson's Disease
Study Description:	This is a randomized, single-blinded, triple crossover study with 3 one-day iTBS, separated by a wash-out period of 3 weeks ¹ , sufficient for physiologic effects of one session of iTBS to return to baseline. Participants will undergo accelerated iTBS to 3 brain regions: medial prefrontal cortex (mPFC) (experimental site), dorsolateral prefrontal cortex (DLPFC) (alternative experimental site), or primary sensory cortex (S1) (control site). Participants will complete symptom questionnaires, neurologic examination and cognitive assessments, and orthostatic vital signs recording before and after each brain stimulation session.
Objectives:	

Primary Objective: Aim 1: To determine whether iTBS to the medial prefrontal cortex (mPFC) produces more robust changes in frontal midline theta (FMT) EEG power in people with Parkinson's disease compared with stimulation at the dorsolateral prefrontal cortex (DLPFC) or the primary sensory cortex (S1). Aim 2: A. To evaluate FMT power correlations with burden of autonomic symptoms in Parkinson's

disease. B. To evaluate FMT power correlations with burden of depression symptoms in Parkinson's disease

Exploratory Objectives:

Aim 3: To evaluate the effect of iTBS on autonomic symptoms one day after, and 4 days after stimulation. Aim 4: To evaluate the effect of iTBS on depression symptoms one day after, and 4 days after stimulation.

Aim 5: To create a database of EEG and TMS data in people with PD for the purpose of future research into novel neurostimulation therapies for PD NMS

Outcome measures:

Primary Outcome Measures: Aim 1: Degree of change of frontal midline theta power on EEG after brain stimulation. Aim 2: Degree of association between autonomic symptoms and frontal midline theta EEG power; Degree of association between depression symptoms and frontal midline theta EEG power.

Exploratory Outcome measures: Aim 3: Change in SCOPA-AUT and OHQ from before to after iTBS; Aim 4: Change in BDI-II from before to after iTBS

Study Population:

Study population will be men and women of all demographic groups with Parkinson's disease age 50-90 years who do not have a diagnosis of severe dementia who reside in North Carolina.

Phase:

N/A (pilot study)

Description of

UNC Medical Center will be the only participating site.

Sites/Facilities Enrolling

Participants:

Description of Study

Participants will undergo three sessions of intermittent theta-burst stimulation (iTBS), an FDA-approved therapy for treatment of depression, while at rest. Stimulation will be delivered to the medial prefrontal cortex, dorsolateral prefrontal cortex, and the primary sensory cortex (one site per stimulation session). Electroencephalography will be collected immediately before and after stimulation, and questionnaires and clinical evaluations will be completed before and after stimulation sessions.

[figure not shown]
Intervention:

Three years

Study Duration:

The total number of contacts per subject, including in-person, telephone, email, and mailings will range from 4-15. Duration of each contact will range from 10 minutes – 2.5 hours. Total duration of an individual subject's participation is expected to be 5-6 hours for informed consent, initial clinical evaluation and screening, questionnaires, and EEG/TMS visit.

1.2 SCHEMA

1.3 SCHEDULE OF ACTIVITIES (SOA)

Procedures	Screening Day -7 to -1	Visit 1, Week 1	Telephone visit, Week 1+1 day	Telephone visit, Week 1+4 days	Study Visit 2 Week 4	Telephone visit, Week 4+1 day	Telephone visit, Week 4+4 days	Study Visit 3 Week 7	Telephone visit, Week 7+1 day	Telephone visit, Week 7+4 days
Informed consent	X									
Demographics	X									
Medical history	X									
Randomization	X									
iTBS + EEG		X			X			X		
Concomitant medication review	X	X			X			X		
MDS-UPDRS	X	X			X			X		
Montreal Cognitive Assessment	X									
Orthostatic Vital signs	X	X			X			X		
Adverse event review and evaluation		X	X	X	X	X	X	X	X	X
Freezing of Gait questionnaire	X	X			X			X		
Epworth Sleepiness Scale	X									
REM sleep disorder questionnaire	X									
OHQ and SCOPA- AUT		X	X	X	X	X	X	X	X	X
Beck Depression Inventory - II		X	X	X	X	X	X	X	X	X
Complete Case Report Forms (CRFs)	X	X	X	X	X	X	X	X	X	X

2 INTRODUCTION

2.1 STUDY RATIONALE

Parkinson's disease (PD) is the second most common neurodegenerative disease in the US. Autonomic dysfunction (AuD) and depression are common non-motor symptoms of PD which are strongly predictive of poor disease outcomes, and lack effective treatments. Non-invasive brain stimulation, such as transcranial magnetic stimulation (TMS), is a safe, effective, FDA-approved treatment for major depression disorder and psychotic disorders, and is undergoing study for treatment of motor symptoms

in PD. Intermittent theta-burst stimulation (iTBS) is a TMS paradigm that has been found to be as effective in fewer treatments than traditional TMS paradigms, and is FDA approved to treat major depression disorder. Few studies have investigated the use of any neurostimulation tool to treat non-motor symptoms of PD. The overarching objective of this study is to determine the feasibility of using transcranial magnetic stimulation to treat AuD and depression in PD. Based on preliminary evidence implicating brain structures (the medial prefrontal cortex and the anterior cingulate gyrus) in both AuD and depression in PD, the central hypothesis in this study is that the medial prefrontal cortex is a major driver of AuD and depression in PD, and an effective brain stimulation target.

2.2 BACKGROUND

Parkinson's disease (PD) is a common, progressive neurodegenerative disease characterized by a combination of motor and non-motor symptoms that is made debilitating by both motor and non-motor symptoms. The prevalence of PD in North Carolina (NC) is about 400 cases per 100,000 among Medicare beneficiaries [1]. Non-motor symptoms (NMS) of PD are common and associated with significant morbidity and mortality². Autonomic nervous system dysfunction, which causes symptoms such as orthostatic hypotension (OH), constipation and gastroparesis, urinary retention or incontinence, and sexual dysfunction, affects more than half of PD patients [2-4], and is strongly predictive of poorer quality of life and overall prognosis [5, 6]. Similarly, refractory depression in PD is a common and disabling NMS³. Unfortunately, both of these NMS have limited treatment options.

Both invasive (Deep brain stimulation, DBS) and more recently non-invasive (transcranial magnetic stimulation, TMS) neurostimulation are used for the clinical and/or experimental treatment of motor symptoms but have yet to be thoroughly investigated in the context of NMS in PD. The development of brain stimulation treatments requires an understanding of structural and functional brain networks⁴⁻⁶. The feasibility of such rational design of brain stimulation is made possible with the growing understanding of brain network dysfunction in PD^{7,8}.

The hypothalamus (HTH), anterior cingulate cortex (ACC), medial prefrontal cortex (mPFC), and insula play key roles in the central autonomic network (CAN), by modulating autonomic function⁹, and in the limbic network where they regulate emotion. Pathology is found in these areas in PD¹⁰. Functional and structural brain MRI studies in PD consistently implicate the CAN, including the mPFC, as a substrate in AuD¹¹⁻¹⁴. Other key nodes of both autonomic and depression networks, such as the dorsolateral prefrontal cortex (DLPFC), remain spared by PD pathology¹⁰. MRI abnormalities in the ACC and mPFC in PD depression mirror findings in PD AuD¹⁵⁻¹⁹.

Our group used resting state functional MRI (rs-fMRI) to study brain correlates of autonomic symptoms in PD¹¹. In a publicly-available database of *early* PD, we found reductions in hypothalamic functional connectivity in PD with high burden of autonomic symptoms¹¹. Our preliminary brain MRI data in people with PD points to central dysregulation in PD autonomic dysfunction, particularly implicating the HTH, ACC, and mPFC (**Fig. 1**, Appendix). Interestingly, these regions of the CAN are also important nodes of the limbic network, implicated in the regulation of mood and emotion²⁰.

Electroencephalography (EEG) provides high temporal resolution for the measurement of brain network dynamics and their modulation by non-invasive brain stimulation²¹⁻²³. EEG correlates of autonomic function in the neurologically healthy localize to frontal midline areas and associate with theta oscillations (4-8 Hz)²⁴⁻²⁸. The majority of these studies are primarily focused on heart rate variability (HRV) responses,

thought to represent sympathetic and parasympathetic autonomic nervous system function, though this is agreed to be an indirect measure and remains controversial²⁹. There are no studies investigating EEG correlates of AuD in PD to our knowledge. *I hypothesize that altered frontal midline theta (FMT) oscillations are a marker of AuD and thus a target for non-invasive brain stimulation.*

TMS is a form of non-invasive neurostimulation used to modulate brain networks. TMS, effective when applied to the dorsolateral prefrontal cortex (DLPFC) or mPFC³⁰, is FDA approved for the treatment of major depressive disorder (MDD). Theta-burst TMS (TBS) was recently developed for treatment of neurologic and psychiatric symptoms. TBS has equivalent if not longer-lasting effects compared with traditional repetitive TMS (rTMS)^{31,32}. Continuous TBS is thought to have inhibitory effects while intermittent TBS (iTBS) has excitatory effects³³. In MDD, iTBS is equivalent or more effective compared with rTMS and has recently been FDA approved^{34,35}.

Studies of effects of TMS on autonomic function exhibit mixed results³⁶. Four studies, including only one study in PD, found that DLPFC stimulation has a positive effect on autonomic function or symptoms³⁷⁻⁴⁰. There has been one study investigating the effect of iTBS on autonomic function⁴¹. In this study, iTBS was applied to the DLPFC in subjects with MDD while concordant HRV was assessed. Intriguingly, this study reported significant heart rate decelerations in the iTBS groups compared to sham (placebo) stimulation, indicating autonomic nervous system engagement. Interestingly, there are no published reports of TMS targeted to CAN structures to probe autonomic function. Taken together, the literature suggests iTBS applied to CAN network nodes, particularly the mPFC which is implicated in PD pathology as well as depression and AuD, may improve AuD by restoring FMT oscillations and top-down control of the CAN.

2.3 RISK/BENEFIT ASSESSMENT

2.3.1 KNOWN POTENTIAL RISKS

Psychological risk

Breach of confidentiality: While there is the potential for breach of confidentiality, all study personnel will minimize this risk to study subjects. All data will be de-identified before analysis, and any treatment outcome data will be treated with strict confidentiality. Electronic data will be stored on password-protected servers within the UNC School of Medicine and any hard-copy data will be stored in locked cabinets in locked offices in the UNC Department of Neurology.

Risk of embarrassment: There is a risk of distress or embarrassment for the participant if they have difficulty performing well on cognitive and physical tests. The research team will take extra care to perform these evaluations in a judgement-free manner, and provide appropriate encouragement to the participant, as is routinely done in a clinical setting. Additionally, we will request that the participant be alone in the examining room with the examiner, without care partner or other persons in the room, while performing these examinations, unless otherwise preferred by the participant, to help minimize this risk.

Physical risk:

Risk of injury and discomfort: Transcranial magnetic stimulation (TMS) is FDA approved for treatment of many neuropsychiatric symptoms in the USA. TMS is not related to electroconvulsive therapy, which applies many orders of magnitude higher stimulation electrical current. The level of electrical stimulation produced by TMS is within the range of activity that is endogenous to the brain. Furthermore, the intensity of stimulation is calibrated to the sensitivity of the individual participant such that the level of stimulation is matched to the naturally occurring brain activity in that individual. In order to monitor side effects, participants will be asked to complete an adverse effects from stimulation questionnaire after each stimulation session. Research personnel supervising the stimulation sessions will also check with the participant periodically during the stimulation session to ensure the participant is comfortable. If any side effects occur that are rated by the participant as stronger than "moderate", or the participant reports severe discomfort during stimulation, the stimulation session will be terminated immediately.

There is a very low theoretical likelihood that stimulation of neuronal circuits can lead to epileptic discharges. To minimize this risk, we will exclude potential participants with personal history of epilepsy or risk factors for epilepsy. If abnormalities on EEG or a seizure is witnessed during the course of the study, a referral will be made to the UNC Department of Neurology for follow up, and/or the participant's treating neurologist will be notified. In the unlikely event that a seizure with loss of consciousness is witnessed during the course of the study, the participant will be instructed not to operate a motor vehicle until cleared by the Department of Motor Vehicles (DMV).

One of the scales that will be administered assess symptoms of depression (BDI-II questionnaire). Upon receiving this questionnaire, the research coordinator will check the scoring for this assessment. If the patient scored in the "severe" range (>28 points), the PI will be notified, and appropriate immediate referrals for care will be made per the patient's preference. The participant's treating neurologist or primary care physician will be immediately notified via a phone call. 911 will be called in the event that a participant is threatening to hurt themselves or others.

Hearing loss is a potential risk of TMS. This is a rare and moderate to severe risk. To protect against hearing loss, ear plugs are worn by the participant and by the technical operator during stimulation sessions.

There have been rare reports of mood episode switches in people with Bipolar disorder after iTBS (from depressed mood to mania or hypomania). This is a rare but potentially severe.

Other potential risks associated with participation in this study include:

- Scalp irritation due to application of the electroencephalogram electrodes to the scalp. This is infrequent and mild.
- Headache and dizziness are rare and mild
- Muscle tightness and twitching during stimulation are very common and mild

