5.2 EXCLUSION CRITERIA

1. Inability to provide informed consent.
2. Severe dementia
3. History of epilepsy or brain surgery
4. Severe tremor or dyskinesia that would interfere with EEG as determined by the PI
5. Parkinson's patients with clinically significant medical or neurological conditions which may be an alternative cause of orthostatic hypotension, such as neuropathy, renal failure, heart failure, cardiac arrhythmias, severe diabetes, or spinal cord injuries
6. We will exclude patients who are treated with medications which can significantly lower blood pressure or heart rate, such as antihypertensive medications, diuretics, and alpha-blocking medications
7. Presence of other known central nervous system disease that may interfere with performance or interpretation of EEG or TMS
8. Presence of any implanted metal devices including, but not limited to, pacemakers, deep brain stimulators, vagal nerve stimulators, bladder stimulators, or cochlear implants.

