6.4 CONCOMITANT THERAPY

For this protocol, a prescription medication is defined as a medication that can be prescribed only by a properly authorized/licensed clinician. Medications to be reported in the Case Report Form (CRF) are concomitant prescription medications, over-the-counter medications and supplements. Information about concomitant medications will be collected in pre-screening procedures, at the screening visit, and at each stimulation visit. Excluded medications include antihypertensive medications, diuretics, and alpha-blocking medications.

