7.2 PARTICIPANT DISCONTINUATION/WITHDRAWAL FROM THE STUDY

Participants are free to withdraw from participation in the study at any time upon request.

An investigator may discontinue or withdraw a participant from the study for the following reasons:

- Significant study intervention non-compliance
- If any clinical adverse event (AE), laboratory abnormality, or other medical condition or situation occurs such that continued participation in the study would not be in the best interest of the participant
- Disease progression which requires discontinuation of the study intervention
- If the participant meets an exclusion criterion (either newly developed or not previously recognized) that precludes further study participation

- There are factors that, in the opinion of the PI, would place the participant at increased physical or psychological risk, or preclude the participant's compliance or completion of the study

The reason for participant discontinuation or withdrawal from the study will be recorded on the Case Report Form (CRF). Subjects who sign the informed consent form and are randomized but do not receive the study intervention may be replaced. Subjects who sign the informed consent form, and are randomized and receive the study intervention, and subsequently withdraw, or are withdrawn or discontinued from the study, will not be replaced.

Safety data will be collected on any participant that is discontinued due to an AE or SAE. Every effort will be made to complete protocol-specific follow up procedures if possible. If voluntary withdrawal occurs, the participant will be asked to continue scheduled evaluations and complete an end-of-study evaluation. Medical and psychological follow up will be coordinated by the research team as described in this protocol. The researcher will make a note to file for all withdrawals.

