8.2 SAFETY AND OTHER ASSESSMENTS

Pre-screening for the study will involve review of the medical chart for the presence of exclusionary criteria, particularly medical conditions and medications, which may put the participant at risk during the study. These criteria will also be reviewed with the participant at the screening visit and at each stimulation session prior to stimulation. Screening will be performed within 21 days of initial study stimulation visit.

Safety will be monitored throughout the study. A stimulation adverse effects questionnaire will be used based on common side effects experienced with TMS. This questionnaire will be administered at the end of each stimulation session. Additionally, participants will be continually asked about their comfort level during stimulation sessions. If a participant reports greater than moderate level of discomfort during stimulation, the stimulation will be immediately discontinued.

The PI will monitor the study for any adverse and serious adverse events. All serious adverse events will be reported to the IRB. Should there be a serious adverse event that occurs that increases the risks to the participants, the study will be stopped and an investigation will be conducted and a findings report generated before the study is resumed. At the time of enrollment, we will ensure we have an active and accurate phone number on file to contact the subject.

Medical follow-up

In the event that a subject is found during the course of the study to need medical or psychological follow-up related to their study involvement, the following procedures will be followed to address their issues.

Medical: For urgent issues, we will direct subjects to the nearest emergency room versus urgent care center for evaluation, based off of the described difficulties and symptoms. For nonurgent (subacute, chronic) issues related to neurologic condition, a follow-up appointment within our department will be scheduled for within 72 hours of the communication. If the issue is unrelated to their movement disorder but also nonurgent, we will communicate with the subject's primary care physician and, when appropriate, disclose necessary information regarding the study protocol should it be relevant to the complaints at hand.

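### Section 2.3.1 promises to exclude people with risk factors for epilepsy, but the exclusion list in 5.2 carries only part of that promise

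*Combined protocol and SAP*

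**What the plan says.** Section 2.3.1 (Known Potential Risks) describes seizure as a theoretical hazard of very low likelihood and names exclusion as the means of limiting it: "To minimize this risk, we will exclude potential participants with personal history of epilepsy or risk factors for epilepsy".

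Section 5.2 (Exclusion Criteria) lists eight items. Item 3 is "History of epilepsy or brain surgery". Item 7 is "Presence of other known central nervous system disease that may interfere with performance or interpretation of EEG or TMS". Item 6 concerns "medications which can significantly lower blood pressure or heart rate, such as antihypertensive medications, diuretics, and alpha-blocking medications", and Section 6.4 repeats the same three drug classes.

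Section 8.2 (Safety and Other Assessments) describes chart pre-screening for "exclusionary criteria, particularly medical conditions and medications, which may put the participant at risk during the study". It adds: "These criteria will also be reviewed with the participant at the screening visit and at each stimulation session prior to stimulation". Among the grounds for withdrawal in Section 7.2 is: "If the participant meets an exclusion criterion (either newly developed or not previously recognized) that precludes further study participation".

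**The concern.** Two current sections of one protocol define the excluded group differently for the same hazard. The broader definition is in the risk discussion. The narrower one is in the list under the heading Exclusion Criteria, which is the natural source for a screening checklist.

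Exclusion is the only preventive step that 2.3.1 gives for seizure; the rest of that paragraph deals with what happens after an event. If staff screen from 5.2, they can enrol and stimulate someone who, according to 2.3.1, will not be in the trial. An ethics committee that relied on 2.3.1 would then be relying on a control broader than the one applied.

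**Working it through.** No figure in the plan bears on this point and no calculation was run. The check is a comparison of texts.

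**Step 1: count what the eligibility sections name.** The eight items of 5.2 concern, in order:

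1. inability to consent
2. severe dementia
3. epilepsy or brain surgery
4. tremor or dyskinesia that would disturb the EEG
5. conditions that could otherwise explain orthostatic hypotension
6. drugs that lower blood pressure or heart rate
7. other central nervous system disease that could affect EEG or TMS
8. implanted metal devices

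One of the eight names epilepsy. None mentions risk factors for it or a past seizure. None gives the investigator a general power to exclude for safety; the PI's judgement in item 4 is limited to movement that disturbs the EEG. None of the six inclusion criteria in 5.1 fills the gap.

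**Step 2: put the same people through both sections.**

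- *Diagnosed epilepsy.* Excluded by 2.3.1 and by 5.2 item 3. The sections agree.
- *Previous brain surgery.* Excluded by 5.2 item 3, whether or not the team counts it as a risk factor under 2.3.1. There is no gap.
- *Known other brain disease that could affect the EEG or TMS.* Excluded by 5.2 item 7. Where such disease is also a risk factor for epilepsy, the sections agree. Item 7 turns on interference with the recording or stimulation, however, and not on seizure risk as such.
- *A single past seizure, with no epilepsy diagnosis and no other known brain disease.* Excluded by 2.3.1 if a past seizure counts as a risk factor, which is the ordinary reading. No item of 5.2 applies. The sections disagree.

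**Step 3: see which list the checks use.** Section 8.2 refers to the exclusionary criteria without a section number. Section 5.2 is the only list under that heading, so it is the natural reference. On that reading, chart pre-screening, the screening visit and each pre-session review all use the list that lacks the item. The reference in 8.2 to conditions and medications that may put participants at risk describes those criteria; it does not add one.

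**Step 4: look for a definition.** The term risk factors for epilepsy appears only in 2.3.1 and is not defined there. Even a screener who applies 2.3.1 has no list to work from.

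**The case against.** The strongest reply is that 2.3.1 is itself protocol text and is worded as a commitment. Section 10.1.8 requires the approved protocol to be followed, and treating neurologists are asked to consider eligibility (5.5 and 6.1.2). A careful team could therefore exclude these people already. This stands in part: the documents show conflicting instructions and do not show that anyone has been wrongly enrolled. It does not remove the conflict, because the two sections give different answers for the same person.

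A second reply is that item 7 and brain surgery already cover much of the group. That also stands, and it is why the gap is partial.

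A reader might infer three stronger things that the documents do not support:

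- *That participants are unprotected if a seizure occurs during the study.* Section 7.2 has further grounds for withdrawal: an adverse event that makes continuing against the participant's interest, and increased risk in the PI's opinion. Section 8.3.2 gives convulsions without hospital admission as an example of an event that may be judged serious. Section 8.2 stops the study after a serious event that raises risk to participants. Section 2.3.1 provides for referral or notification after a seizure or an abnormal EEG. These do not depend on the wording of 5.2.
- *That the plan wrongly omits drugs that lower the seizure threshold.* Section 2.3.1 does not mention such drugs. Section 6.4 says "Excluded medications include antihypertensive medications, diuretics, and alpha-blocking medications", which matches the blood-pressure purpose of item 6. Whether any drug counts as a risk factor is for the team to decide.
- *That a known number of participants is at risk.* The documents give neither the share of candidates with a risk factor nor a seizure rate. The amount of stimulation such a person would receive measures exposure and shows no harm.

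**Conclusion.** The point holds as an internal inconsistency with a safety consequence. A person can be eligible under 5.2 and excluded under 2.3.1, and a lone past seizure is the clear example. The gap is partial because brain surgery and item 7 cover some of the group, and the protocol itself rates the hazard as very unlikely. Its size in participants cannot be stated from the documents.

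The conclusion rests on two readings: that the exclusionary criteria in 8.2 are those of 5.2, and that a past seizure is a risk factor for epilepsy. It is more than missing detail, because following 5.2 as written admits people whom the protocol says it keeps out. It should be corrected. It does not show that safeguards after enrolment are weakened.

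**What to change.** Extend criterion 3 of 5.2 to cover a history of epilepsy, any past seizure or other risk factor for epilepsy (on a short list set by the team), or brain surgery. The checks already in 8.2 would then apply it at pre-screening, at screening and before each session.

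The cost is one edited line and a few extra screen failures. Medical history is already taken at screening (Section 1.3), so no visit or test is added.

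If the team meant only diagnosed epilepsy, the alternative is to delete the mention of risk factors from 2.3.1, so that the stated control is the one applied.

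A sentence in 7.1 on whether stimulation continues after a seizure or an epileptiform EEG would be a helpful clarification. It is optional, since 7.2 and 8.2 already allow withdrawal or a study stop.
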